6.4 Other Safety Parameters

Data from the early termination visit or unscheduled visits will be listed only and will not be shown in summary tables by time point. All tables will be presented by treatment group and overall. Vital signs will be analyzed for Screening, Visit 3 and Visit 5:

- Diastolic blood pressure
- Systolic blood pressure
- Pulse rate
- Temperature

The following data will be listed only:

- Pregnancy test
- Local tolerability
- Local tolerability – post vaccination
- Symptom-directed physical examination
- System-based physical examination

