8.5 Treatment Period

8.5.1 Visit 1 (day 0)

Subjects found to be eligible will return to site for Visit 1 within 28 days after the screening visit. Inclusion and exclusion criteria will be checked again and (in case of changes since the screening visit) the medical history will be updated. Symptom-directed physical examination, system-based assessment (only if necessary according to findings in symptom-directed physical exam) and vital signs (systolic and diastolic blood pressure, pulse and body temperature) will be recorded. In addition, the subjects will be asked regarding changes in

concomitant medications since the last visit. A serum pregnancy test will be performed in all women.

Blood samples for baseline immunogenicity assessments (measles and Chikungunya antibody ELISA, PRNT₅₀) and isolation of serum for passive transfer will be drawn from an appropriate forearm or cubital vein. For T-cell assays blood samples will be collected and peripheral blood mononuclear cells (PBMCs) will be prepared. For details on laboratory sampling and testing, see section 8.11.

Subjects will be randomised to treatment group A, B, C, D or E and receive their first MV-CHIK vaccination.

The subjects' diaries will be explained and handed over. Subjects will be asked to report their body temperature and any adverse event in these diaries for 7 days, starting 6 hours after the injection.

After observation of the subjects for two hours, local reactions and adverse events (if any occurred) will be recorded.

Blood pressure and pulse rate will be checked, and participants will be discharged only if the investigating physician considers it to be safe for them to leave the department.

The subjects are invited to return to study site for Visit 2 on study day 14 (\pm 1 day).

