8.5.3 Visit 3 (day 28 \pm 5 days)

Subjects will be invited to return to site for Visit 3, 23 to 33 days after Visit 1.

The investigator or designee will examine local tolerability (of previous vaccination site) and ask about any new concomitant medications or AEs occurred since the last visit.

In addition, symptom-directed physical examination, system-based assessment (only if necessary according to findings in symptom-directed physical exam) and vital signs (systolic and diastolic blood pressure, pulse rate and body temperature) will be recorded.

A serum pregnancy test will be performed in all women.

Blood samples will be taken for clinical chemistry, haematology and coagulation parameters and a urine sample will be collected for urinalysis.

Additional blood samples for immunogenicity assessments (measles and Chikungunya ELISA, PRNT₅₀) and isolation of serum for passive transfer will be drawn from an appropriate vein. For T-cell assays blood samples will be collected and PBMCs will be prepared. For details on laboratory sampling and testing, see section 8.11.

Subjects will receive their second vaccination of MV-CHIK or placebo, according to their randomised treatment group.

The subjects' diaries will be explained and handed over. Subjects will be asked to report their body temperature and any adverse event in these diaries for 7 days, starting 6 hours after the injection.

After observation of the subjects for two hours, local reactions and adverse events (if any occurred) will be recorded.

Blood pressure and pulse rate will be measured, and participants will be discharged only if the investigating physician considers it to be safe for them to leave the department.

The subjects are invited to return to study site for Visit 4 on study day 42 (\pm 5 days).

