11.4 Vital Signs and Body Temperature

Systolic and diastolic blood pressure and pulse rate as well as body temperature will be recorded at screening and Visit 1, 3 and 5 with the subject at rest in a sitting position.

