12.3 Methods of Statistical Safety Analysis

The analysis of safety will be performed by means of descriptive measures in the Safety Population. Solicited and unsolicited AEs (local and systemic) will be analysed descriptively.

AEs and concomitant diseases will be coded using the MedDRA coding dictionary.

Solicited AEs (reactogenicity):

Solicited local and systemic AEs gathered by the subjects' diaries will be summarised for the 7-day period, by AE grading (mild, moderate, severe) and by treatment group. The number and percentage of subjects with AEs will be presented. Fisher exact tests will be provided for a comparison of AE rates between treatment groups in summary tables.

Unsolicited AEs:

Separately, the number and percentage of subjects with unsolicited/spontaneous adverse events (AEs), medically-attended AEs (MAEs) and serious adverse events (SAEs) will be presented for each treatment group overall, and by system organ class/preferred term, by AE grade, and relatedness. Fisher exact tests will be provided for a comparison of AE rates between treatment groups.

Laboratory values and vital signs as well as changes in laboratory values from baseline will be analysed descriptively by time point and treatment group.

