4. BASELINE EVALUATION

For the preliminary analysis baseline data (screening visit, VS) will be presented for the Safety and mITT population by treatment group and overall. For the final analysis all tables will be repeated for the PP population. In case populations do not differ, tabulations will not be repeated.

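### SAP 6.4 leaves Visit 1 out of the vital-sign tables and specifies no table for the post-injection blood pressure and pulse checks

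*Combined protocol and SAP*

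**What the plan says.** **Collection.** Protocol 11.4 sets the visits: "Systolic and diastolic blood pressure and pulse rate as well as body temperature will be recorded at screening and Visit 1, 3 and 5". The schedule in SAP 1.6 likewise marks vital signs at Visit 1. Protocol 8.5.1 describes the Visit 1 reading before randomisation and injection.

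A further check follows the two-hour observation. At Visit 1: "Blood pressure and pulse rate will be checked, and participants will be discharged only if the investigating physician considers it to be safe". At Visit 3: "Blood pressure and pulse rate will be measured, and participants will be discharged only if the investigating physician considers it to be safe". Neither check includes temperature.

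**Analysis.** Protocol 12.3 commits to this: "Laboratory values and vital signs as well as changes in laboratory values from baseline will be analysed descriptively by time point and treatment group". SAP 6.4 narrows it: "Vital signs will be analyzed for Screening, Visit 3 and Visit 5". Tables 1.4.38 to 1.4.41 (systolic pressure, diastolic pressure, pulse, temperature) are laid out by visit, with no pre-dose or post-dose level.

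**Baseline.** SAP section 4 reads: "For the preliminary analysis baseline data (screening visit, VS) will be presented for the Safety and mITT population by treatment group and overall". Table 1.2.1.2, which gives vital signs at baseline, is therefore a screening table. Listing 1.4.37 shows vital signs by subject, visit and date, with no clock time and no pre-dose or post-dose field.

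**The concern.** Visit 1 is the day of the first vaccination and supplies the vital signs taken closest before it. Leaving it out is a stated rule in SAP 6.4, not a missing detail. It does not match the SAP's own schedule, nor SAP 2.13, which says the analyses follow the protocol. The list of visits is the one SAP 6.3 uses for laboratory data. It suits laboratory data, which are not taken at Visit 1, and does not suit vital signs, which are. That it was carried over from 6.3 is an inference; the mismatch is there either way.

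At stake is whether the safety tables can describe blood pressure and pulse on the day of an injection. Safety is part of the primary objective (protocol 5.1). The highest dose studied, 1×10^6 TCID50, is nominally twice the top of the range that protocol 4.5 gives for earlier trials, 5×10^5. A reader of the study report would reasonably look for a before-and-after view on vaccination days and would not find one in the specified tables.

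**Working it through.** The plan states no figure on this point. The check sets the collection schedule against the tables and then dates each tabulated row.

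**Scheduled against tabulated**

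| Reading | Collected (protocol 8.5, 11.4; SAP 1.6) | Table specified (SAP 6.4, section 7) |
|---|---|---|
| Screening | Yes | Yes |
| Visit 1, before injection | Yes | No |
| Visit 1, after two-hour observation (blood pressure, pulse) | Yes, as a discharge check | No |
| Visit 3, before injection | Yes | One Visit 3 row; reading not stated |
| Visit 3, after two-hour observation (blood pressure, pulse) | Yes, as a discharge check | No separate row |
| Visit 5 | Yes | Yes |

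Visits with scheduled vital signs: 4. Visits tabulated: 3. Post-injection checks: 2. Post-injection checks with a specified table: 0.

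**Does another table bring Visit 1 back?** No. Table 1.2.1.2 uses screening, and the by-visit tables follow 6.4. Listing 1.4.37 is not restricted to the three visits, so Visit 1 values may appear there as individual records.

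**Which Visit 3 reading?** Protocol 8.5.3 uses the term vital signs for the set taken before the injection, which includes temperature. The later check has blood pressure and pulse only. SAP 6.4 lists all four parameters, which fits the pre-dose set, but the SAP does not say so.

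**How far the tabulated rows lie from an injection, if Visit 3 is the pre-dose reading**

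- Screening: 1 to 28 days before the first injection.
- Visit 3: 23 to 33 days after the first injection (28 ± 5).
- Visit 5: nominally 56 − 28 = 28 days after the second injection. At the window limits the interval runs from 51 − 33 = 18 to 61 − 23 = 38 days.

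No row then falls within two weeks after an injection. If the Visit 3 row were instead the post-injection reading, it would fall about two hours after the second injection, with no same-visit value to set against it. Under either reading the Day 0 values are absent.

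**Number of records.** Visit 1 pre-dose: 60 sets, one per subject. Post-injection checks: 60 subjects × 2 injections = 120. This is an upper bound. It assumes that every subject receives both injections and that the checks are entered as data.

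**The case against.** The strongest reply is that the later blood pressure and pulse readings are discharge checks and not planned measures of effect. Protocol 8.5.5 has a similar check before discharge at Visit 5, where nothing is injected. Protocol 11.4 and the schedules list vital signs once per visit. Nothing in the documents says that the checks enter the eCRF as vital-sign records. This stands: it would be wrong to say that the SAP drops post-injection data, because they may never have been meant as data.

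Three more points also stand. Listing 1.4.37 may show Visit 1. Temperature is recorded in the diary for seven days after each injection, with fever graded, and adverse events are recorded after the two-hour observation and tabulated. The benefit/risk section (protocol 4.6) names no haemodynamic concern.

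A reader might also infer more than the documents support:

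- **That vaccine and placebo readings are blended at Visit 3.** The tables are by treatment group, and every subject in a group is assigned the same second injection. Only the overall column pools them.
- **That Group D against Group E on Day 28 is the only placebo contrast.** Groups A to C also receive vaccine that day while Group E receives placebo, and diary temperature gives a further comparison. D and E are simply the pair alike in first dose and formulation.
- **That an outdated screening value distorts a change from baseline.** Protocol 12.3 promises change from baseline for laboratory values only, and the SAP plans no such table for vital signs.
- **That protocol 12.3 is plainly breached.** It says by time point without saying every time point.

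The reply does not explain why the scheduled Visit 1 vital signs are left out of the tables, or which Visit 3 reading is shown.

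**Conclusion.** The point holds as a minor analysis gap. SAP 6.4 omits from the tables one of the four visits at which vital signs are scheduled, and that visit is the day of first vaccination. No table is specified for either post-injection blood pressure and pulse check, and the Visit 3 row is undefined, though probably pre-dose. As written, the blood pressure and pulse tables contain no pre-dose Day 0 value and no specified reading soon after an injection.

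The omission of Visit 1 rests on the text alone. The statement about post-injection readings is that they have no specified table, not that they were discarded; the count of 120 applies only if they are captured. Severity is low: vital signs are not among the listed endpoints, their analysis is descriptive, there are 12 subjects per group, and other outputs cover part of acute safety.

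**What to change.** In SAP 6.4 and Tables 1.4.38 to 1.4.41:

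1. Add Visit 1 pre-dose and name it as the reference value for vital signs.
2. State that the main Visit 3 row is the pre-dose reading. A similar line for Visit 5 would settle which of its two blood pressure and pulse readings is used.
3. Where captured, tabulate the post-injection blood pressure and pulse at Visits 1 and 3 as separate, labelled rows by treatment group. Temperature stays with the main readings.
4. Add a clock time or a pre-dose/post-dose field to Listing 1.4.37. The SAP already gives local tolerability after vaccination its own listing with date and time, so there is a pattern to follow.

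The cost is a few lines of SAP text and a few table rows. No new measurement is needed. If the discharge checks are not already entered as data, one eCRF line is needed at each of the two vaccination visits. If they cannot be captured, items 1, 2 and 4 can still be done, and the report should say that post-injection blood pressure and pulse were not tabulated.

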7. LIST OF TABLES, DATA LISTINGS AND FIGURES

7.1 List of Tables

No. for IA	No. for FA	Legend	Content
Overall Subject Information			
1.1.1.1	2.1.1.1	Subject Overview (Safety Population)	
 • Randomized • Safety Population • mITT Population • PP Population
1.1.1.2	2.1.1.2	Subjects by Visit (Safety Population)	
1.1.1.3	n/a	Vaccinated Subjects and Reason for missed Vaccinations (Safety Population)	
 • Number of subjects that received first vaccination • Number of subjects that received second vaccination • Number of subjects that missed any vaccination • Reason for missing any vaccination
1.1.1.4	2.1.1.4	Protocol Deviations by Deviation Type (Safety Population)	
 • Any major PD • Any major PD by category • Any minor PD • Any minor PD by category
1.1.1.5	2.1.1.5	Study Status (Safety Population)	
 • Visit attendance status • Primary reason for early termination
1.1.1.6	n/a	Number of Screening Failures and Reasons	
 • Number of screening failures • Reason for screening failure
1.1.2.2-1.1.2.5	2.1.2.2-2.1.2.5	Repeat tables x.1.1.1-x.1.1.5 for mITT population (if not the same as Safety Population)	
1.1.3.2-1.1.3.5	n/a	Repeat tables x.1.1.1-x.1.15 for PP population	
Baseline Evaluation			
1.2.1.1	n/a	Summary Table of Demographic Information (Safety Population)	
 • Age • Gender • Race • Height [cm] • Weight [kg]
1.2.1.2	n/a	Vital Signs at Baseline (Safety Population)	
 • Systolic blood pressure [mmHg] • Diastolic blood pressure [mmHg] • Pulse rate [beats/min] • Temperature [C]
1.2.1.3	n/a	Medical History Entry by SOC and PT (Safety Population)	
1.2.1.4	n/a	Prior Medications by ATC Level 2 and 3 (Safety Population)	
1.2.1.5	n/a	Concomitant Medications and by ATC Level 2 and 3 (Safety Population)	
1.2.1.6	n/a	Vaccination History by ATC Level 2 and Level 3 (Safety Population)	

Adapted from:

Page 20 of 29

STAT03_A Statistical Analysis Plan

Version 6.0, Effective Date 16-Feb-2018

Confidential and intellectual property of Assign DMB. No part of this document or its contents may be duplicated, referenced, published or otherwise disclosed in any form or by any means without prior written consent of Assign DMB.

06CJDX

1.2.2.1-1.2.2.6	n/a	Repeat tables x.2.1.1-x.2.1.6 for mITT population (if not the same as Safety Population)	
1.2.3.1-1.2.3.6	n/a	Repeat tables 2.1.1-x2.1.6 for PP population (if not the same as Safety Population)	
Immunogenicity Results			
Primary Endpoint			
1.3.1.1	2.3.1.1	GMT of anti-Chikungunya PRNT ₅₀ Antibody 28 days after last MV-CHIK vaccination (mITT Population)	
1.3.1.2	2.3.1.2	ANOVA with fixed factor treatment group for GMT of anti-Chikungunya PRNT ₅₀ Antibody 28 days after last MV-CHIK vaccination (mITT Population)	
Anti-Chikungunya PRNT₅₀ Antibody			
1.3.1.3	2.3.1.3	GMT of anti-Chikungunya PRNT ₅₀ Antibody by Visit (mITT Population)	
 • Preliminary Analysis: Visit 1, 3 and 5 • Final Analysis : All available time points
1.3.1.4	2.3.1.4	ANOVA for GMT of anti-Chikungunya PRNT ₅₀ Antibody between treatment groups by Visit (mITT Population)	
 • Preliminary Analysis: Visit 1, 3 and 5 • Final Analysis : All available time points
1.3.1.5	2.3.1.5	Seroconversion rate for Anti-Chikungunya PRNT ₅₀ Antibody by Visit (mITT Population)	
 • Preliminary Analysis: Visit 1, 3 and 5 • Final Analysis : All available time points
Chikungunya-ELISA Antibodies			
1.3.1.6	2.3.1.6	GMT of Chikungunya-ELISA Antibodies 28 days after last MV-CHIK vaccination (mITT Population)	
1.3.1.7	2.3.1.7	ANOVA for GMT of Chikungunya-ELISA Antibodies between treatment groups 28 days after last MV-CHIK vaccination (mITT Population)	
n/a	2.3.1.8	GMT of Chikungunya-ELISA Antibodies by Visit (mITT Population)	
 • All available time points
n/a	2.3.1.9	ANOVA for GMT of Chikungunya-ELISA Antibodies between treatment groups by Visit (mITT Population)	
 • All available time points
n/a	2.3.1.10	Seroconversion rate of Chikungunya-ELISA Antibodies by Visit (mITT Population)	
 • All available time points
Measles-ELISA antibodies			
n/a	2.3.1.11	GMT of Measles-ELISA Antibodies 28 days after last MV-CHIK vaccination (mITT Population)	
 • All available time points

Adapted from:

Page 21 of 29

STAT03_A Statistical Analysis Plan

Version 6.0, Effective Date 16-Feb-2018

Confidential and intellectual property of Assign DMB. No part of this document or its contents may be duplicated, referenced, published or otherwise disclosed in any form or by any means without prior written consent of Assign DMB.

06CJDX

1.3.1.1 - 1.3.1.7	1.3.2.1 - 1.3.2.11	Repeat tables for PP Population	
Safety Results			
Extent of Exposure			
1.4.1.	2.4.1	Extent of Exposure (Safety Population)	
 • Study duration • Treatment duration
Adverse Events			
1.4.2	n/a	Summary Table of solicited and unsolicited Adverse Events (Safety Population)	
Number of subjects with:
 
 • Any AEs • Any related AEs • Any severe AEs • Any related severe AEs • Any SAEs • Any related SAEs • Any medically attended AEs • Any related medically attended AEs • Any AEs leading to study discontinuation • Any AEs leading to second vaccination not administered
1.4.3	n/a	Summary Table of solicited Adverse Events (Safety Population)	
 • Any solicited AEs • Any related solicited AEs • Any severe solicited AEs • Any related severe solicited AEs • Any solicited SAEs • Any related solicited SAEs • Any medically attended solicited AEs • Any related medically attended solicited AEs • Any solicited AEs leading to study discontinuation • Any solicited AEs leading to second vaccination not administered
1.4.4	n/a	Summary Table of solicited local Adverse Events (Safety Population)	
 • Any solicited local AEs • Any related solicited local AEs • Any severe solicited local AEs • Any related severe solicited local AEs • Any solicited local SAEs • Any related solicited local SAEs • Any medically attended solicited local AEs • Any related medically attended solicited local AEs • Any solicited local AEs leading to study discontinuation • Any solicited local AEs leading to second vaccination not administered
1.4.5	n/a	Summary Table of solicited systemic Adverse Events (Safety Population)	
 • Any solicited systemic AEs • Any related solicited AEs • Any severe solicited AEs

Adapted from:

Page 22 of 29

STAT03_A Statistical Analysis Plan

Version 6.0, Effective Date 16-Feb-2018

Confidential and intellectual property of Assign DMB. No part of this document or its contents may be duplicated, referenced, published or otherwise disclosed in any form or by any means without prior written consent of Assign DMB.

06CJDX

			
 • Any related severe solicited systemic AEs • Any solicited systemic SAEs • Any related solicited systemic SAEs • Any medically attended solicited systemic AEs • Any related medically attended solicited systemic AEs • Any solicited systemic AEs leading to study discontinuation • Any solicited systemic AEs leading to second vaccination not administered
1.4.6	n/a	Summary Table of unsolicited Adverse Events (Safety Population)	
 • Any unsolicited AEs • Any related unsolicited AEs • Any severe unsolicited AEs • Any serious unsolicited AEs • Any medically attended unsolicited AEs • Any related severe unsolicited AEs • Any related serious unsolicited AEs • Any related medically attended unsolicited AEs • Any unsolicited AEs leading to second vaccination not administered • Any unsolicited AEs caused study discontinuation
1.4.7	n/a	Subjects with at least one Adverse Event classified by Maximum Severity (Safety Population)	
Solicited Adverse Events			
1.4.8	n/a	Subjects with solicited local Adverse Events by Symptom (Safety Population)	
1.4.9	n/a	Subjects with solicited systemic Adverse Events by Symptom (Safety Population)	
1.4.10	n/a	Subjects with solicited Adverse Events classified by Maximum Severity (Safety Population)	
1.4.11	n/a	Subjects with solicited local Adverse Events by Symptom classified by Maximum Severity (Safety Population)	
1.4.12	n/a	Subjects with solicited systemic Adverse Events by Symptom classified by Maximum Severity (Safety Population)	
Unsolicited Adverse Events			
1.4.13	n/a	Subjects with unsolicited Adverse Events by SOC and PT (Safety Population)	
1.4.14	n/a	Subjects with related unsolicited	

Adapted from:

Page 23 of 29

STAT03_A Statistical Analysis Plan

Version 6.0, Effective Date 16-Feb-2018

Confidential and intellectual property of Assign DMB. No part of this document or its contents may be duplicated, referenced, published or otherwise disclosed in any form or by any means without prior written consent of Assign DMB.

06CJDX

		Adverse Events by SOC and PT (Safety Population)	
1.4.15	n/a	Subjects with severe unsolicited Adverse Events by SOC and PT (Safety Population)	
1.4.16	n/a	Subjects with serious unsolicited Adverse Events by SOC and PT (Safety Population)	
1.4.17	n/a	Subjects with medically attended unsolicited Adverse Events by SOC and PT (Safety Population)	
1.4.18	n/a	Subjects with related severe unsolicited Adverse Events by SOC and PT (Safety Population)	
1.4.19	n/a	Subjects with related serious unsolicited Adverse Events by SOC and PT (Safety Population)	
1.4.20	n/a	Subjects with related medically attended unsolicited Adverse Events by SOC and PT (Safety Population)	
1.4.21	n/a	Subjects with unsolicited Adverse Events leading to second Vaccination not administered (Safety Population)	
1.4.22	n/a	Subjects with unsolicited Adverse Events caused study discontinuation (Safety Population)	
1.4.23	n/a	Subjects with at least one unsolicited Adverse Event by Maximum Severity (Safety Population)	
1.4.24	n/a	Subjects with at least one medically attended unsolicited Adverse Event by Maximum Severity (Safety Population)	
1.4.25	n/a	Subjects with at least one unsolicited Adverse Event by Causality (Safety Population)	
1.4.26	n/a	Subjects with at least one medically attended unsolicited Adverse Event by Causality (Safety Population)	
1.4.27	n/a	Subjects with at least one serious unsolicited Adverse Event by Causality (Safety Population)	
Laboratory Parameters			
1.4.28	n/a	Absolute Values for Hematology Parameters by Parameter and Visit (Safety Population)	
1.4.29	n/a	Absolute Values for Clinical	

Adapted from:

Page 24 of 29

STAT03_A Statistical Analysis Plan

Version 6.0, Effective Date 16-Feb-2018

Confidential and intellectual property of Assign DMB. No part of this document or its contents may be duplicated, referenced, published or otherwise disclosed in any form or by any means without prior written consent of Assign DMB.

06CJDX

		Chemistry Parameters by Parameter and Visit (Safety Population)	
1.4.30	n/a	Absolute Values for Coagulation Parameters by Parameter and Visit (Safety Population)	
1.4.31	n/a	Absolute Changes from Baseline for Hematology Parameters by Parameter and Visit (Safety Population)	
1.4.32	n/a	Absolute Changes from Baseline for Clinical Chemistry Parameters by Parameter and Visit (Safety Population)	
1.4.33	n/a	Absolute Changes from Baseline for Coagulation Parameters by Parameter and Visit (Safety Population)	
1.4.34	n/a	Subjects with Hematology Parameters Outside Normal Range by Parameter and Visit (Safety Population)	
1.4.35	n/a	Subjects with Clinical Chemistry Parameters Outside Normal Range by Parameter and Visit (Safety Population)	
1.4.36	n/a	Subjects with Coagulation Parameters Outside Normal Range by Parameter and Visit (Safety Population)	
1.4.37	n/a	Urine Laboratory Results by Parameter and Visit (Safety Population)	
1.4.38	n/a	Absolute Changes from Baseline for pH and Specific Gravity by Visit (Safety Population)	
Other Safety Parameters			
1.4.38	n/a	Systolic Blood Pressure [mmHg] by Visit (Safety Population)	
1.4.39	n/a	Diastolic Blood Pressure [mmHg] by Visit (Safety Population)	
1.4.40	n/a	Pulse Rate [beats/min] by Visit (Safety Population)	
1.4.41	n/a	Body Temperature [°C] by Visit (Safety Population)	

